# Deep Vein Thrombosis and Pulmonary Embolism

Venous thromboembolic events (predominantly deep venous thrombosis and pulmonary embolism) have occurred in patients with MM treated with lenalidomide combination therapy. A significantly increased risk of DVT and PE was observed in patients with MM who were treated with REVLIMID and dexamethasone therapy in a clinical trial.

# **Allergic Reactions**

Angioedema, anaphylaxis, and serious dermatologic reactions including Stevens-Johnson syndrome

(SJS) and toxic epidermal necrolysis (TEN) have been reported. These events can be fatal. Patients with a prior history of Grade 4 rash associated with thalidomide treatment should not

Version Date: 01/01/2024

receive REVLIMID. REVLIMID interruption or discontinuation should be considered for Grade 2-3 skin rash. REVLIMID must be discontinued for angioedema, Grade 4 rash, exfoliative or bullous rash, or if SJS or TEN is suspected and should not be resumed following discontinuation for these reactions.

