Fall to < 25 x 10  /L	Fall to < 25 x 10  /L Hold both Lenalidomide and Carfilzomib, follow CBC weekl Hold prophylactic anti-coagulation.	
Return to $\geq 25 \times 10^9/L$	Resume lenalidomide at next dose reduction	Resume carfilzomib at full dose*
Subsequent fall to < 25 x 10  /L	Hold both Lenalidomide and Carfilzomib, follow CBC weekly. Hold prophylactic anti-coagulation.	
Return to ≥ 25 x 10  /L	Resume lenalidomide at next dose level reduction  Resume carfilzomib at full dose	

\*Carfilzomib may be dose reduced at the clinical discretion of investigator

Neutropenia (Absolute Neutrophil Count)	Lenalidomide	Carfilzomib
Falls to $< 0.5 \times 10^9/L$ or to $< 1.0 \times 10^9/L$ with fever		filzomib. Add filgrastim if Grade 3 are of 38.3°C or sustained temperature de 4. Follow CBC weekly
Returns to $\geq 1.0 \times 10^9/L$	Resume Lenalidomide at next dose reduction.	Resume Carfilzomib at full dose*
Subsequent drop to $< 0.5 \text{ x}$ $10^9/\text{L}$ or to $< 1.0 \text{ x}$ $10^9/\text{L}$ with fever		
Returns to $\geq 1.0 \times 10^9/L$	Resume Lenalidomide at next dose reduction.	Resume Carfilzomib at full dose*

\*Carfilzomib may be dose reduced at the clinical discretion of investigator.

- 3.3.3 Non-Hematologic Toxicity: Induction Phase
- 3.3.3.1 Toxicity ≥ grade 3 will require appropriate study drug to be held until resolved to ≤ Grade 1 unless specified below. Investigator will determine which drug will be held based on side effect profile and clinical judgment.
- 3.3.3.2 Once toxicity has resolved ≤ grade 1, subsequent doses will be reduced at next dose level (according to table in section 3.3.1) if the adverse event was deemed to be treatment related by the PI. If the adverse event was deemed to be unrelated to treatment, the patient may continue the full dose.
- 3.3.3.3 Readily reversible electrolyte and metabolic abnormalities, infections or diarrhea controlled by appropriate therapy are exempt.
- 3.3.3.4 Patients with Grade 3 or higher peripheral neuropathy, Grade 3 or higher non-blistering rash or blistering rash of any grade, grade 3 or higher hypersensitivity reactions will be removed from protocol therapy.

Lenalidomide Toxicities	Dosing Modifications
Blistering Rash (Any Grade)	Discontinue lenalidomide and remove patient from therapy

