Venous thrombosis/ embolism	Hold lenalidomide and start therapeutic anticoagulation. Restart lenalidomide at investigator's discretion at current dose level.
Renal Dysfunction CrCl based on Cockcroft-Gault. (Alternatively, MDRD or CKD- epi formulas may be used to estimate eGFR as more accurate indictors of renal dysfunction than	
 
CrCl 31-50 ml/min – Dose reduce lenalidomide to 10 mg daily from Days 1-21
 
CrCl ≤30 mL/min (not requiring dialysis) – Dose reduce Lenalidomide to 15 mg every 48 hours
 
CrCl ≤30 mL/min (requiring dialysis) – Decrease
 
Lenalidomide to 5 mg daily and on dialysis days give
 

indictors of renal dysfunction than CrCl in discrepant cases)	Lenalidomide to 5 mg daily and on dialysis days give lenalidomide dose after dialysis.

Carfilzomib Toxicities	Dosing Modifications
Allergic Reaction/Hypersensitivity	Grade 2: Hold carfilzomib until ≤ Grade 1 and resume at full carfilzomib dose
Tumor Lysis Syndrome (≥ 3 of the following: ≥50% increase in creatinine, uric acid, or phosphate; ≥30% increase in potassium; ≥20% decrease in calcium; or 2-fold increase in LDH	Hold carfilzomib until all abnormalities in serum chemistries have resolved. Resume at full dose
Herpes zoster or simplex of any grade	Hold carfilzomib until lesions are dry. Resume at full dose
Neuropathy	Grade 2 treatment emergent neuropathy with pain: Hold carfilzomib until resolved to $\leq$ Gr 1 without pain. Then restart at next dose level reduction.
Congestive Heart Failure	Any subject with symptoms of congestive heart failure, whether or not drug related, must have the dose held until resolution or return to baseline. After which, treatment may continue at reduced dose or patient may be withdrawn from therapy.
Renal Toxicity: Serum creatinine ≥ 2 × baseline, or Creatinine clearance less than 15 mL/min, or creatinine clearance decreases to less than or equal to 50% of baseline, or need for hemodialysis	Withhold dose and continue monitoring renal function (serum creatinine or creatinine clearance).  If attributable to carfilzomib, resume when renal function has recovered to within 25% of baseline; start at 1 dose level reduction. If not attributable to carfilzomib, dosing may be resumed at the discretion of the physician. For patients on hemodialysis receiving carfilzomib, the dose is to be administered after the hemodialysis procedure.

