# 3.3.5 Hematologic Toxicity: Extended Dosing Phases I and II

- 3.3.5.1 On day 1 (or within 7 days prior to day 1) of every third cycle during extension phase, patients must meet the following criteria or dose modify based on dose reductions in table 3.3.4:
  - ANC  $\geq 1.0 \times 10^9 / L$

Version Date: 01/01/2024

• Platelet count  $>50 \times 10^9$ /L during cycles 9 and beyond

If these conditions are not met on Day 1 of every third cycle, treatment will not be initiated until the toxicity has resolved or returned to baseline. If there is no resolution after 2 weeks of withholding treatment or up to 3 weeks for infection related treatment, the subject will go off therapy.

3.3.5.2 If a patient develops thrombocytopenia or neutropenia during the cycle, then the following actions would take place (see Thrombocytopenia/Neutropenia table below).

Thrombocytopenia	Lenalidomide				
Fall to < 25 x 10  /L	Hold Lenalidomide, follow CBC weekly. Hold prophylactic anti-coagulation.				
Return to $\geq 25 \times 10^9/L$	Resume lenalidomide at next dose reduction if deemed drug related				
Subsequent fall to < 25 x 10  /L	Hold Lenalidomide. Hold prophylactic anti-coagulation				
Return to $\geq 25 \times 10^9/L$	Patient will go off therapy if deemed drug related				

Neutropenia (Absolute Neutrophil Count)	Lenalidomide			
Falls to < 0.5 x 10  /L or to < 1.0 x 109/L with fever	Hold Lenalidomide. Add filgrastim if Grade 3 with fever (single temperature of 38.30 or sustained temperature of 380 for > 1 hour) or Grade 4. Follow CBC weekly			
Returns to $\geq 1.0 \times 10^9/L$	Resume Lenalidomide at next dose reduction.			
Subsequent drop to $< 0.5 \times 10^9/L$ or to $< 1.0 \times 109/L$ with fever	Hold Lenalidomide. Add filgrastim if Grade 3 with fever or Grade 4. Follow CBC weekly			
Returns to $\geq 1.0 \times 10^9/L$	Patient will go off therapy if deemed drug related			

- 3.3.6 Non-Hematologic Toxicity- Extended Dosing Phase
- 3.3.6.1 Toxicity ≥ grade 3 will require study drug to be held until resolved to ≤ Grade 1 or baseline unless specified below.

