- 3.3.6.2 Once toxicity has resolved ≤ grade 1 or baseline, subsequent doses will be reduced at next dose level (according to table in Section 3.3.4) if the adverse event was deemed to be treatment related by the PI. If the adverse event was deemed to be unrelated to treatment, the patient may continue the full dose. In the case of renally adjusted doses, dosing modifications are made according to table below.
- 3.3.6.3 Readily reversible electrolyte and metabolic abnormalities or infections controlled by appropriate therapy are exempt.

Version Date: 01/01/2024

Common Lenalidomide Toxicities	Dosing Modifications				
Non-Blistering Rash	
 
If Grade 3, hold lenalidomide dose and restart at next dose reduction once rash improves to ≤ Grade 1
 
If Grade 4, discontinue lenalidomide and remove patient from therapy
 
				
Blistering Rash (Any Grade)	Discontinue lenalidomide and remove patient from therapy				
Venous thrombosis/embolism	Hold lenalidomide and start therapeutic anticoagulation. Restart lenalidomide at investigator's discretion at current dose level.				
Renal Dysfunction: CrCl based on Cockcroft-Gault. (NOTE: Alternatively, MDRD or CKD-epi formulas may be used to estimate eGFR as more accurate indictors of renal dysfunction than CrCl in discrepant cases.)	
 
CrCl 31-50 ml/min – Dose reduce lenalidomide to 10 mg daily from Days 1-21
 
CrCl ≤30 mL/min (not requiring dialysis) – Dose reduce Lenalidomide to 15 mg every 48 hours and see carfilzomib dosing below.
 
CrCl ≤30 mL/min (requiring dialysis) – Decrease Lenalidomide to 5 mg daily and on dialysis days dose lenalidomide after dialysis.
 
				

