# 3.6.1 Criteria for removal from protocol therapy

- Patients with medically concerning grade 3 or 4 adverse events related to drug therapy may be taken off therapy at the discretion of the principal investigator.
- Patients require more than 2 dose reductions of carfilzomib.
- Toxicity has not resolved after 2 weeks of withholding treatment or up to 3 weeks for infection related treatment
- Grade 3 non-blistering rash or blistering rash of any grade
- Grade 3 neuropathy
- Grade 3 hypersensitivity reaction
- Diagnosis of posterior reversible encephalopathy (PRES) or thrombotic microangiopathy (TMA)
- Patient completes the protocol (as outlined in Section 3.2)
- Progression of disease
- Patient chooses to go off therapy
- The principal investigator may remove patient from protocol therapy if deemed necessary due to medical conditions, compliance, etc.
- Patient becomes pregnant.

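### In extended dosing, Section 3.3.6 restarts lenalidomide after Grade 3 or higher angioedema, or Grade 3 exfoliative or suspected SJS/TEN rash without blistering, where Section 14.2.2 forbids resumption and 3.6.1 can require removal.

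*Combined protocol and SAP*

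**What the plan says.** **Section 14.2.2, Allergic Reactions.** Lenalidomide "must be discontinued for angioedema, Grade 4 rash, exfoliative or bullous rash, or if SJS or TEN is suspected and should not be resumed". Within that list only the plain-rash item carries a grade. The sentence before it is softer: "REVLIMID interruption or discontinuation should be considered for Grade 2-3 skin rash". The same paragraph warns that reactions of this kind may be fatal.

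**Section 3.3.6, extended dosing.** The general rule in 3.3.6.1 is "Toxicity ≥ grade 3 will require study drug to be held until resolved to ≤ Grade 1 or baseline unless specified below". For events judged treatment related, 3.3.6.2 then says "subsequent doses will be reduced at next dose level (according to table in Section 3.3.4"); by the table in 3.3.4 that is a step from 10 mg to 5 mg. The lenalidomide table in 3.3.6 has rows for non-blistering rash (Grade 3: hold, then restart one level lower; Grade 4: discontinue and remove) and for blistering rash of any grade (discontinue and remove). It has no row for angioedema, hypersensitivity, exfoliative rash or suspected SJS/TEN.

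**Section 3.3.3, induction.** A hold is mandatory from Grade 3 (3.3.3.1). Under 3.3.3.4, patients with Grade 3 or higher non-blistering rash or blistering rash of any grade leave therapy, and those with "grade 3 or higher hypersensitivity reactions will be removed from protocol therapy".

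**Section 3.6.1, both phases.** The removal list includes Grade 3 non-blistering rash, blistering rash of any grade, and "Grade 3 hypersensitivity reaction". It does not limit these entries to one phase.

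**The concern.** A site managing a toxicity would normally open the tables in 3.3. For the reactions named in 14.2.2, those tables lead in extended dosing to a different outcome from the drug-information section, and in part from the removal list. Depending on the section consulted, the same event ends in a restart at a lower dose, a permanent stop, or removal from protocol therapy. The protocol does not say which section governs.

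Toxicity is a secondary objective (1.1.2), and Section 10.2 commits to full safety reporting on all evaluable patients. If the rule is ambiguous, a restart after one of these reactions, or a removal because of it, cannot be interpreted with confidence. It is also unclear which of the two would have been a deviation under 8.8.

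**Working it through.** No arithmetic applies. The check sets the rules side by side by reaction, grade and phase. Section 3.3 never names angioedema, exfoliative rash, SJS or TEN, so each is placed under the nearest rule there: the rash rows for skin events and the general rule for angioedema. Events are taken as judged treatment related.

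| Event | 3.3 | 3.6.1 | 14.2.2 | Result |
|---|---|---|---|---|
| Extended dosing, angioedema Grade 3 or higher | No row; general rule: hold, then resume one level lower | Removal if classed as Grade 3 hypersensitivity | Stop, do not resume | Incompatible |
| Extended dosing, exfoliative rash without blistering, Grade 3 | Rash row: hold, then restart one level lower | Removal | Stop, do not resume | Incompatible |
| Extended dosing, suspected SJS/TEN without blistering, rash Grade 3 | Rash row: hold, then restart one level lower | Removal | Stop, do not resume | Incompatible |
| Either phase, the same reactions at Grade 1-2 | No lenalidomide hold required | No specific criterion | Stop; no grade given | Thresholds differ |
| Either phase, bullous or blistering rash, any grade | Discontinue and remove | Removal | Stop, do not resume | Consistent |
| Either phase, Grade 4 rash | Removal | Listed from Grade 3 | Stop, do not resume | Consistent |
| Induction, rash or hypersensitivity Grade 3 or higher | Removal (3.3.3.4) | Listed from Grade 3 | Stop for the named reactions | Consistent |

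1. The second row is the clearest case. A Grade 3 exfoliative rash without blisters meets the 3.3.6 row that orders a restart, the 3.6.1 line that orders removal, and the 14.2.2 sentence that forbids resumption. A site cannot carry out all three.
2. The angioedema case arises because 3.3.6 has no row for it, so the general hold-and-reduce rule applies by default.
3. Part of the second and third rows is a wider disagreement: 3.3.6 restarts and 3.6.1 removes for any Grade 3 non-blistering rash. For ordinary Grade 2-3 rash, 14.2.2 only asks that interruption or discontinuation be considered, so it does not settle that disagreement.
4. In the fourth row, 3.3 sets the grade from which a hold is mandatory. It does not order that lenalidomide be continued below that grade, so both sections can be followed at once.

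**The case against.** The case on the other side has several parts.

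- **Section 3.6.1 already covers Grade 3 hypersensitivity.** If angioedema is classed that way, as its place under Allergic Reactions suggests, 3.6.1 and 14.2.2 both point away from a restart, and the principal investigator also has discretion to remove a patient. This is fair, but it leaves 3.3.6 saying the opposite with no precedence stated, and discretion does not reconcile two explicit rules.
- **Section 14.2.2 is drug information.** It is nonetheless in the protocol body and is worded as an obligation.
- **Treatment is over.** The Study Calendar footnotes (3.4), Section 5.1.1 and Appendix C record that all participants had finished cycle 32 by February 6, 2023, and the current version is dated 01/01/2024. This stands. A reader might infer that patients can still be re-exposed under this text, but the documents do not support that.

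Other stronger readings also fail:

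- **A stop ordered at any grade.** Section 14.2.2 does not say this; it is inferred from the absence of a grade.
- **A flat contradiction at Grade 1-2.** Section 3.3 does not order continuation at those grades.
- **The Grade 2 allergic-reaction row as a conflicting lenalidomide rule.** That row reads "Grade 2: Hold carfilzomib until ≤ Grade 1 and resume at full carfilzomib dose". It belongs to the carfilzomib table, and 3.3.1.1 treats dose reductions of the two drugs separately. Its silence on lenalidomide is not a conflict.
- **A conflict over SJS/TEN as a whole.** Once there is blistering, the any-grade blistering rule already leads to discontinuation and removal.
- **Uncertainty over whether a stop also means leaving therapy.** In extended dosing lenalidomide is the only study drug, so the question has little content there.

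**Conclusion.** The inconsistency is real but narrow. It is direct in extended dosing for three situations: Grade 3 or higher angioedema, Grade 3 exfoliative rash without blistering, and suspected SJS/TEN without blistering graded 3. At Grade 1-2, in both phases, the sections use different thresholds, which is worth aligning but is not a contradiction.

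The conclusion rests on three readings: that events not named in 3.3 fall under its general rule or rash rows; that the absence of a grade in 14.2.2 means no threshold was intended there; and that no precedence between the sections is stated. For induction, the finding of consistency at Grade 3 or higher assumes that angioedema is classed as hypersensitivity.

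No count of affected patients is given, because the documents report no incidence of these reactions. The primary endpoint is not shown to be affected. With dosing complete, the practical value lies in a coherent current text and in interpreting past discontinuations, restarts and deviations.

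**What to change.** Reconcile 3.3.3 (3.3.3.1, 3.3.3.4 and the lenalidomide table), 3.3.6 (3.3.6.1, 3.3.6.2 and the lenalidomide table), 3.6.1 and 14.2.2. For angioedema, exfoliative rash and suspected SJS/TEN, give one instruction that covers:

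- the grade threshold, or that there is none;
- whether lenalidomide may be resumed;
- whether the patient leaves protocol therapy.

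An explicit row in each of the two lenalidomide tables, with matching lines in 3.6.1 and 14.2.2, would do this. The row should say whether the general hold-and-reduce rule applies to these events. The differing treatment of Grade 3 non-blistering rash in 3.3.6 and 3.6.1 should be settled at the same time. Which rule stands is for the clinical team to decide.

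The safety report should state which rule was used to classify past discontinuations, restarts and deviations after these reactions. The cost is protocol wording, with no added visits, tests or patients.

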# **Tumor Lysis Syndrome**

Fatal instances of tumor lysis syndrome have been reported during treatment with lenalidomide. The patients at risk of tumor lysis syndrome are those with high tumor burden prior to treatment. These patients should be monitored closely and appropriate precautions taken.

# Most common adverse reactions (≥20%)

Fatigue, neutropenia, constipation, diarrhea, muscle cramp, anemia, pyrexia, peripheral edema, nausea, back pain, upper respiratory tract infection, dyspnea, dizziness, thrombocytopenia, tremor and rash.

# Rare and Serious adverse reactions

Myocardial infarction, myocardial ischemia, cardiac failure, gastrointestinal hemorrhage, intestinal obstruction; meningitis, infections of the skin, joints, and kidney; abnormal levels of blood sugars and electrolytes, hypoxia, hepatocellular injury.

# 14.2.3 Formulation and preparation

Lenalidomide will be supplied as capsules for oral administration. Bristol Myers Squibb (BMS) will provide lenalidomide 5, 10, 15 and 25 mg capsules for the Induction Phase of the protocol and for the extended dosing phase(s).

# 14.2.4 Stability and Storage

Lenalidomide should be stored at room temperature away from direct sunlight and protected from excessive heat and cold.

# 14.2.5 Administration procedures

Bristol Myers Squibb (BMS) will supply Revlimid® (lenalidomide) to the Clinical Center Pharmacy to be dispensed to study participants at no charge through the REMS® program. Lenalidomide will be shipped directly to patients or picked up directly from the Clinical Center pharmacy. Bottles will contain a sufficient number of capsules for one cycle of dosing; no more than a one-month supply of lenalidomide may be dispensed at one time.

# 11.2.6 Incompatibilities

Results from human in vitro metabolism studies and nonclinical studies show that REVLIMID is neither metabolized by nor inhibits or induces the cytochrome P450 pathway suggesting that lenalidomide is not likely to cause or be subject to P450- based metabolic drug interactions in man.

### Digoxin

When digoxin was co-administered with lenalidomide, the digoxin AUC was not significantly

Version Date: 01/01/2024

different; however, the digoxin Cmax was increased by 14%. Periodic monitoring of digoxin plasma levels, in accordance with clinical judgment and based on standard clinical practice in patients receiving this medication, is recommended during administration of lenalidomide.

### Warfarin

Co-administration of multiple doses of 10 mg of lenalidomide had no effect on the single dose pharmacokinetics of R- and S-warfarin. Co-administration of single 25-mg dose warfarin had no effect on the pharmacokinetics of total lenalidomide. Expected changes in laboratory assessments of PT and INR were observed after warfarin administration, but these changes were not affected by concomitant lenalidomide administration.

# Concomitant Therapies That May Increase the Risk of Thrombosis

Erythropoietic agents, or other agents that may increase the risk of thrombosis, such as estrogen containing therapies, should be used with caution in MM patients receiving lenalidomide with dexamethasone.

### 14.3 DEXAMETHASONE

# 14.3.1 Source

Dexamethasone will be provided from commercial sources by the NIH Clinical Center Pharmacy Department.

# 14.3.2 Toxicity

### Common

Cardiovascular: Hypertension

Dermatologic: Atrophic condition of skin, Finding of skin healing, Impaired

Endocrine metabolic: Cushing's syndrome, Decreased body growth

Gastrointestinal: Disorders of gastrointestinal tract

Immunologic: At risk for infection Musculoskeletal: Osteoporosis

Ophthalmic: Cataract (5%), Raised intraocular pressure (25%)

Psychiatric: Depression, Euphoria Respiratory: Pulmonary tuberculosis

Serious

Endocrine metabolic: Hyperglycemia, Primary adrenocortical insufficiency

Ophthalmic: Conjunctival hemorrhage (22%), Glaucoma, Vitreous detachment (2%)

# 14.3.3 Formulation and preparation

Oral Tablet (Scored): 4 mg

Injection, solution, as sodium phosphate: 4 mg/mL (1 mL, 5 mL, 30 mL)

# 14.3.4 Administration procedures

Oral: Administer with meals to decrease GI upset.

*Version Date:* 01/01/2024

I.V.: Administer intravenously over 10 minutes.

# 14.3.5 Incompatibilities

Contraindicated: Praziquantel (theoretical), Rotavirus Vaccine, Live (established)

Major: Aldesleukin (theoretical), Bupropion (theoretical), Darunavir (theoretical), Dasatinib (theoretical), Etravirine (theoretical), Fosamprenavir (theoretical), Imatinib (theoretical), Ixabepilone (theoretical), Lapatinib (theoretical), Nilotinib (theoretical), Quetiapine (probable), Romidepsin (theoretical), Sunitinib (theoretical), Temsirolimus (theoretical), Thalidomide (probable).

Version Date: 01/01/2024

